#### 6.4.1.3 On-DBT AEs

Frequency tables of on-DBT AEs are provided for the DBT safety analysis set by SOC and PT for the following endpoints:

- AEs by worst intensity (secondary objective #7)
- AEs related to study drug by worst intensity
- SAEs (secondary objective #7)
- AEs leading to study drug discontinuation
- Hepatic-related AEs (secondary objective #9)

- Hepatic-related AEs leading to study drug discontinuation (secondary objective #9)
- Potential drug abuse AEs, displayed in alphabetical order by worst intensity and PT without SOC
- Cardiovascular AEs
- Suicidality AEs.

Frequency tables of AEs by SOC and PT display AEs in descending order of zavegepant pooled within SOC and PT, unless otherwise specified.

## 6.4.1.4 On-OL Zavegepant AEs

Frequency tables of on-OL zavegepant AEs are provided for the OL zavegepant safety analysis set by SOC and PT for the same endpoints listed in Section 6.4.1.3.

## 6.4.1.5 Follow-up AEs

Frequency tables of follow-up AEs are provided by SOC and PT for the follow-up safety analysis set for the following endpoints:

- AEs by worst intensity
- SAEs.

# 6.4.2 Laboratory Tests

Laboratory tests are analyzed using results from local laboratory tests reported on CRFs and the external central laboratories (i.e., Cerba Research and ACM Global Laboratories). Central laboratories report both laboratory collection date and time, whereas CRFs capture only laboratory collection date.

Laboratory tests of clinical interest are collected at the following visits:

- Hematology: Screening; Pre-randomization; Weeks 4, 12, 16, 24, 48, and 64; and early termination
- Serum chemistry: Screening; Pre-randomization; Weeks 4, 12, 16, 24, 48, and 64; and early termination. Exceptions are for the following:
  - LFTs (ALT, AST, ALP, TBL, direct bilirubin, indirect bilirubin): All visits except Baseline
  - Lipids (total cholesterol, high-density lipoprotein [HDL] cholesterol, low-density lipoprotein [LDL] cholesterol, triglycerides) and HBA1c: Screening; Weeks 12 and 64; and early termination
- Urinalysis: Screening; Weeks 12 and 64; and early termination.

The following by-subject laboratory test listings are provided for the enrolled analysis set:

- Laboratory test results (SI units). The listing displays all test results over time for subjects with select findings (grade 3 to 4 laboratory test abnormalities or positive pregnancy tests) at any time point.
- LFT values and ratios to ULN (i.e., ALT, AST, TBL and ALP) for SI units. The listing displays all LFT results over time for subjects with select LFT elevations (ALT or AST > 3x ULN; ALP or TBL > 2x ULN) at any time point.

Refer to the Core SAP for laboratory tests of clinical interest for analyses (including identification of those with toxicity grades) and TLF contents.

# 6.4.2.1 Laboratory Test Abnormalities

Frequency tables of the worst (highest) laboratory test abnormality for each graded laboratory test are provided for the following safety analysis periods and analysis sets:

- On-DBT for the DBT safety analysis set
- On-OL zavegepant for the OL zavegepant safety analysis set
- Follow-up for the follow-up safety analysis set.

Grade 3 to 4 results support other secondary objective #7.

#### 6.4.2.2 LFT Elevations

#### LFT Elevations: Cumulative, Mutually Exclusive, and Composite

Frequency tables of LFT elevations are provided for the following safety analysis periods and analysis sets:

- On-DBT for the DBT safety analysis set
- On-OL zavegepant for the OL zavegepant safety analysis set
- On-DB or OL zavegepant for the DB or OL zavegepant safety analysis set
- Follow-up for the follow-up safety analysis set.

Results support secondary objective #8 and exploratory objectives #8 and #9.

A confidence level of 97.5% is used for CIs.

#### **LFT Plots**

By-subject longitudinal LFT plots are provided for the safety analysis set with select LFT elevations in any safety analysis period. Study weeks are defined as study day/7, where study day is derived from the laboratory test collection date (see Section 7.3). Each figure also displays DB study drug and OL zavegepant dosing days using symbols along the x-axis (see Section 9.4), and denotes additional study milestones (e.g., start of the on-DBT safety analysis period, start of the OL zavegepant safety analysis period, and start of the follow-up safety analysis period) using vertical lines with their corresponding descriptions in footnotes.

# 6.4.2.3 Laboratory Test Changes from Baseline over Time

The table of values and changes from baseline in hematology and serum chemistry laboratory tests is provided by treatment group, zavegepant pooled, placebo pooled, and overall for the safety analysis set at the following time points: baseline; each scheduled visit through Week 12 and EOT in the on-DBT safety analysis period; each scheduled visit from Week 14 through Week 64 and EOT in the on-OL zavegepant safety analysis period; and each scheduled visit in the follow-up safety analysis period. Results for zavegepant pooled and placebo pooled are displayed only at baseline and time points in the on-DBT safety analysis period. Results for overall are displayed only at baseline and time points in the on-OL zavegepant and follow-up safety analysis periods.

Note that scheduled visits vary according to laboratory test.

Refer to the Core SAP for (1) handling multiple values in an analysis visit window or on the same laboratory collection date, and (2) deriving the EOT value in an on-treatment safety analysis period. Note that Cerba Research provides sample code (vial/tube identifier), whereas ACM Global Laboratories provide accession identifier.

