Target Population:	This study will recruit male and female subjects, who are at least 18 years of age, and who have at least a one-year history of chronic migraine (with or without aura). The migraine diagnosis must be in accordance with the International Classification of Headache Disorders, 3 rd edition. Per subject report, subjects must have migraine onset prior to age 50, history of chronic migraine onset prior to age 65, migraine attacks that last 4-72 hours (if not treated), and at least 15 headache days per month over the last 3 months before Screening, of which at least 8 are migraine days, and with at least one non-headache day per month during the last 3 months before Screening.
Number of Subjects:	Approximately 2900 subjects will be screened in order to randomize approximately 1440 subjects. It is estimated that approximately 1200 subjects will be entered into the OLE Phase.
Objectives (Primary):	To compare the efficacy of oral zavegepant to placebo as a preventive treatment for chronic migraine, as measured by the mean reduction from the Observation Phase in the number of migraine days per month over the entire DBT Phase. (In this study, a month is defined as 28 days or 4 weeks.)

Study Design:

[figure not shown]
All subjects will participate in a 28-day Observation Phase. During the Observation Phase, subjects will treat migraines with standard of care migraine medications. Subjects will report migraine occurrence, migraine pain features and associated symptoms (e.g., pain intensity, nausea, photophobia and phonophobia), and will document use of acute migraine medication in an electronic diary (eDiary).

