Eligible subjects will be randomized 2:2:1:1 across 4 treatment groups in the DBT Phase: zavegepant 100 mg (n = 480); zavegepant 200 mg (n = 480); placebo matching zavegepant 100 mg (n = 240); or placebo matching zavegepant 200 mg (n = 240). Subjects will take the assigned study drug every day for 12 weeks. Subjects participating in PK draws will be required to dose in person at the study site to assess PK at the Week 4 and Week 8 Visits. Subjects will report migraine occurrence, migraine pain features and associated symptoms, and use of acute migraine medication in the eDiary during the DBT Phase. Upon completion of the DBT Phase, subjects may enter the 52-week OLE Phase and receive the assigned dose from the DBT Phase (either zavegepant 100 mg or 200 mg). If subjects do not enter the OLE Phase, they will have visits in the Follow-up Phase at approximately 2 weeks and 8 weeks after the last visit in the DBT Phase. Subjects who complete the OLE Phase or who discontinue early during the OLE Phase will also have visits in the Follow-up Phase at approximately 2 weeks and 8 weeks after the last visit in the OLE Phase.

[figure not shown]
Subjects will also report concomitant medication, including standard of care migraine medication (both prophylactic and acute), taken throughout the entire study in the concomitant medication paper diary.

STUDY SCHEMATIC

Observation, DBT, and Follow-up Phases

OLE and Follow-up Phases

Approximately 60 Weeks

TABLE OF CONTENTS

	IARY OF CHANGES	
CONFI	IDENTIALITY AND INVESTIGATOR STATEMENT	5
STUDY	Y SUMMARY (SYNOPSIS)	6
STUDY	Y SCHEMATIC	8
TABLE	E OF CONTENTS	9
LIST O	OF TABLES	12
	OF FIGURES	
LIST O	OF ABBREVIATIONS	13
1 IN'	TRODUCTION AND RATIONALE	15
1.1	BackgroundBackground	15
1.2	CGRP's Role in Migraine	16
1.3	Product Development Background	16
1.3.1	Clinical Experience	16
1.3.1.1	Single Ascending Dose (SAD) BHV3500-101	
1.3.1.2	Multiple Ascending Dose Study (MAD) BHV3500-102	
1.3.1.3	Phase 2/3 Dose Ranging Study (BHV3500-201)	17
1.3.1.4	BHV3500-103	
1.3.1.5	BHV3500-107	
1.3.2	Summary of Animal Data with Oral and Sublingual Zavegepant	17
1.4	Study Rationale	18
1.4.1	Study Design Rationale	18
1.4.2	Dose Selection Rationale	19
1.4.3	Other Rationale Related to the Compound / Study	19
1.4.4	Research Hypothesis	19
2 ST	UDY OBJECTIVES	20
2.1	Primary Objective(s)	20
2.2	Secondary Objective(s)	20
	Exploratory Objective(s)	
	UDY ENDPOINTS	
	Primary Endpoint(s)	
	Secondary Endpoint(s)	
	Definition of Migraine Days	

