1.4.1 Study Design Rationale

This is a 12-week multicenter, randomized, double-blind, placebo-controlled evaluation of the efficacy and safety of zavegepant tablet taken every day for the prevention of migraine in subjects with a history of chronic migraine. Eligible subjects who complete the 12-week DBT Phase may continue to the 52-week OLE Phase.

Approximately 1440 subjects will be randomized and assigned treatment in the DBT Phase. Subjects will be randomized in a 2:2:1:1 ratio across 4 treatment groups: zavegepant 100 mg (n = 480); zavegepant 200 mg (n = 480); placebo matching zavegepant 100 mg (n = 240); or placebo matching zavegepant 200 mg (n = 240). Randomization will be stratified by use of stable prophylactic migraine medication through randomization (yes or no; see Section 7.2). Upon completion of the 12-week DBT Phase, eligible subjects may continue to the 52-week OLE Phase. In the OLE Phase, subjects will continue to take the dosing regimen they were randomized to during the DBT Phase (i.e., zavegepant 100 mg or 200 mg daily).

During the DBT Phase, subjects will be instructed to follow one of the following 2 dosing regimens:

• Take four (4) 25 mg soft gelatin capsules of blinded study drug every calendar day, if randomized to the zavegepant 100 mg or placebo matching zavegepant 100 mg treatment group

• Take eight (8) 25 mg soft gelatin capsules of blinded study drug every calendar day, if randomized to the zavegepant 200 mg or placebo matching zavegepant 200 mg treatment group.

If subjects have a migraine, they may treat the migraine with permitted acute migraine medication (see Section 5.5.2) and continue to take study drug on their regular schedule.

Subjects who enter the OLE Phase will continue to take the dosing regimen they were randomized to during the DBT Phase (i.e., 100 mg zavegepant daily or 200 mg zavegepant daily).

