5 POPULATION

5.1 Number of Subjects

It is anticipated that up to approximately 2900 subjects may be screened in order to randomize up to approximately 1440 subjects to study drug (zavegepant 100 mg, zavegepant 200 mg, placebo matching zavegepant 100 mg, or placebo matching zavegepant 200 mg) in the DBT Phase. It is estimated that approximately 1200 subjects will enter the OLE Phase.

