#### 6.1.1.1 Tables

Treatment group presentation in tables by analysis set is shown in Table 4. Exceptions are specified in subsequent sections as needed.

Table 4 Treatment Group Presentation in Tables by Analysis Set

Analysis Set	Number of Columns	Abbreviated Treatment Group
Enrolled	1	Overall
Full, DBT efficacy, migraine, DBT safety, interim safety by treatment group, {zavegepant pooled}, {placebo pooled}, and {overall}	4 to 7	ZAV 100 mg ZAV 200 mg {ZAV Pooled} PBO 100 mg PBO 200 mg {PBO Pooled}
OL zavegepant safety by OL zavegepant dose and overall	3	{Overall} OL ZAV 100 mg OL ZAV 200 mg Overall
DB or OL zavegepant safety by DB or OL zavegepant dose and overall	3	DB ZAV or PBO 100 mg/OL ZAV 100 mg DB ZAV or PBO 200 mg/OL ZAV 200 mg Overall
Follow-up safety by treatment group/OL zavegepant status and overall	6	DB ZAV 100 mg/OL ZAV 100 mg DB ZAV 200 mg/OL ZAV 200 mg DB PBO 100 mg to OL ZAV 100 mg DB PBO 200 mg to OL ZAV 200 mg DB PBO Pooled No OL ZAV Overall

"ZAV Pooled" is defined as the DB zavegepant 100 mg and DB zavegepant 200 mg treatment groups combined. "PBO Pooled" is defined as the DB placebo 100 mg and DB placebo 200 mg treatment groups combined. "DB PBO X mg to OL ZAV X mg" denotes as-treated DB placebo X mg subjects in the OL zavegepant safety analysis set (X = 100 or 200), and "DB PBO Pooled No OL ZAV" denotes as-treated DB placebo pooled subjects not in the OL zavegepant safety analysis set; note that these 3 placebo groups add to the "PBO Pooled" group.

Results for study population also include overall treatment group (see Sections 6.2 and 6.4).

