## 6.4 Safety

Safety parameters include the following: deaths; AEs; laboratory tests; vital signs; physical measurements; electrocardiograms (ECGs); and Columbia-Suicidality Severity Rating Scale (C-SSRS.

Tables of safety endpoints are provided according to safety analysis period and analysis set as follows:

- On-DBT for the DBT safety analysis set by treatment group, zavegepant pooled, and placebo pooled
- Post-DBT pre-OL zavegepant for the interim safety analysis set by treatment group, zavegepant pooled, placebo pooled, and overall
- On-OL zavegepant for the OL zavegepant safety analysis set by OL zavegepant dose and overall
- On-DB or OL zavegepant for the DB or OL zavegepant safety analysis set by DB or OL zavegepant dose and overall
- Follow-up for the follow-up safety analysis set by treatment group/OL zavegepant status and overall.

Treatment group is as-treated according to Section 6.1.1.1.

Measurements are slotted into analysis periods and analysis visits using the following steps:

- 1) Measurements are slotted into the pretreatment, on-treatment safety, and follow-up safety analysis periods.
- 2) Measurements are slotted into analysis visits in the analysis periods listed in the previous step (see Table 5). This does not apply to AEs.
- 3) Measurements in the on-treatment safety analysis period are slotted further into the on-DBT, post-DBT pre-OL zavegepant, and on-OL zavegepant safety analysis periods.

Refer also to the Core SAP for details about measurement slotting. See Sections 6.2.5, 7.2 and 7.3 for definitions of baseline, analysis periods, and analysis visit windows, respectively.

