# 6.4.3.1 Vital Sign and Physical Measurement Changes from Baseline over Time

The table of values and changes from baseline in vital signs and physical measurements is provided by treatment group, zavegepant pooled, placebo pooled, and overall for the safety analysis set at the following time points: baseline; each scheduled visit through Week 12 and EOT in the on-DBT safety analysis period; each scheduled visit from Week 14 through Week 64 and EOT in the on-OL zavegepant safety analysis period; each scheduled visit in the follow-up safety analysis period. Results for zavegepant pooled and placebo pooled are displayed at baseline and time points in the on-DBT safety analysis period. Results for overall are displayed only at baseline and time points in the on-OL zavegepant and follow-up safety analysis periods.

Refer to the Core SAP for (1) handling multiple values in an analysis visit window or on the same measurement date, and (2) deriving the EOT value in an on-treatment safety analysis period.

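### Follow-up rows of the laboratory and vital-sign change tables stay in double-blind columns, so the placebo columns mix never-exposed subjects with subjects recently off open-label zavegepant

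*SAP*

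**What the plan says.** SAP 6.4.2.3 specifies one table of laboratory values and changes from baseline, "provided by treatment group, zavegepant pooled, placebo pooled, and overall for the safety analysis set at the following time points: baseline; each scheduled visit" through the double-blind treatment (DBT) phase, the OLE and follow-up. SAP 6.4.3.1 does the same for vital signs and physical measurements and also ends with "each scheduled visit in the follow-up safety analysis period". SAP 4.2 defines the treatment groups as the four double-blind groups. Both sections tie the pooled zavegepant and pooled placebo columns to the baseline and on-DBT rows, and both show an overall column at baseline, on-OL and follow-up. The follow-up rows therefore sit under ZAV 100 mg, ZAV 200 mg, PBO 100 mg, PBO 200 mg and overall.

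The general rule for follow-up tables in SAP 6.4 is different: "Follow-up for the follow-up safety analysis set by treatment group/OL zavegepant status and overall". Table 4 (SAP 6.1.1.1) gives that layout separate columns for placebo subjects who moved to open-label zavegepant, by dose. It adds a column, DB PBO Pooled No OL ZAV, which "denotes as-treated DB placebo pooled subjects not in the OL zavegepant safety analysis set".

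Under Protocol 4.3.3, placebo subjects who enter the OLE receive zavegepant at the dose their placebo matched. Under Protocol 4.3.4, all randomized subjects should attend follow-up about 2 and 8 weeks after the last visit of their last treatment phase.

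**The concern.** In the follow-up rows of these two tables, a column headed placebo no longer describes subjects without drug. It holds some subjects who never took zavegepant and others who stopped up to 52 weeks of it a few weeks earlier. If mean liver tests or vital signs shift after withdrawal, part of that shift appears under placebo, and the gap between the placebo and zavegepant columns shrinks.

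The affected parameters matter. Liver function tests and vital signs are collected at both follow-up visits, and hepatic safety appears among the secondary objectives. These are also the only tables specified in the SAP that show continuous change at follow-up. A mean shift below the abnormality thresholds has no other summary there.

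**Working it through.** **1. Which rows are mixed.** Baseline and on-DBT rows are correctly described by double-blind group. In the on-OL rows every subject is on zavegepant. Only the follow-up rows combine exposed and never-exposed subjects under one placebo label. For laboratory tests these rows are in practice liver function tests (the protocol's LFT panel also includes CK), because the Protocol 4.3 schedules and SAP 6.4.2 place hematology and general chemistry at no follow-up visit.

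**2. Inputs.** The documents state no percentage on this point, so there is no figure of theirs to reproduce. They give two planning counts: "It is estimated that approximately 1200 subjects will enter the OLE Phase" (Protocol 5.1) and "Approximately 1440 subjects will be randomized and assigned treatment in the DBT Phase" (Protocol 1.4.1). The planned group sizes agree with the second: 480 + 480 + 240 + 240 = 1440. Placebo is 240 + 240 = 480.

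**3. Share of placebo subjects who are post-OLE at follow-up.** Assume equal OLE entry by arm, and equal follow-up attendance by entrants and non-entrants.
- Share: 1200/1440 = 0.833.
- All placebo: 480 × 0.833 = 400 post-OLE; 480 − 400 = 80 never on open-label drug.
- Each placebo column: 240 × 0.833 = 200 post-OLE; 240 − 200 = 40 never on open-label drug.

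**4. Without equal entry.** There are 1440 − 1200 = 240 planned non-entrants. If all are placebo subjects, the share is (480 − 240)/480 = 50%. If none are, it is 100%. The two counts alone fix nothing tighter.

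**5. Unequal attendance.** Keep equal entry, s = 0.833. Let a₁ be the attendance of entrants and a₂ that of non-entrants (assumed values, not in the documents). The share is p = s·a₁ / (s·a₁ + (1 − s)·a₂).

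**6. Contrast kept.** Suppose subjects who stopped zavegepant show a mean change D, never-exposed subjects show none, and post-OLE placebo subjects resemble the zavegepant columns. The zavegepant columns then show D, the placebo columns show p·D, and the visible contrast is (1 − p)·D.

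| Assumption | p | Contrast kept, 1 − p |
|---|---|---|
| Equal entry, equal attendance | 0.833 | 0.167 |
| Attendance 0.5 entrants, 0.9 non-entrants | 0.735 | 0.265 |
| Attendance 0.6 entrants, 0.9 non-entrants | 0.769 | 0.231 |
| Attendance 0.9 entrants, 0.6 non-entrants | 0.882 | 0.118 |
| Attendance 0.9 entrants, 0.5 non-entrants | 0.900 | 0.100 |
| All 240 non-entrants on placebo, equal attendance | 0.500 | 0.500 |
| No non-entrants on placebo | 1.000 | 0 |

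**7. What other output shows.** The follow-up tables of AE overview (6.4.1.2), AEs and SAEs (6.4.1.5), laboratory abnormalities (6.4.2.1), LFT elevations (6.4.2.2), and vital-sign and ECG abnormalities (6.4.3.2, 6.4.4.2) use the follow-up safety analysis set, and so take Table 4's split columns. The laboratory listings in 6.4.2 and the LFT plots in 6.4.2.2 cover only subjects with selected findings, and 6.4.3 names no vital-sign listing. The split of mean changes cannot be rebuilt from the output the SAP describes.

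**The case against.** The case for leaving the tables alone has several fair parts.

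- **Exceptions are allowed.** SAP 6.1.1.1 lets later sections depart from Table 4. The split is specified for the follow-up safety analysis set, whereas these two tables use the wider safety analysis set. A reader might infer a flat contradiction; the documents do not support that. It is a departure for which no reason is given.
- **The plan already drops the pooled comparison after the DBT phase.** This stands: no pooled placebo column appears at follow-up, so only PBO 100 mg and PBO 200 mg are affected.
- **No inference hangs on it.** SAP 5 says significance will not be evaluated even for the primary and secondary endpoints, and the safety objectives cover the DBT and OLE phases. This stands, and it keeps the point small.
- **Recovery can be read down a column,** from the end of open-label treatment to follow-up. This holds only in part. The on-OL rows contain OLE subjects alone, while the follow-up rows below them also include subjects who never entered the OLE.
- **Splitting does not yield a clean contrast.** This stands. Protocol 4.3.3 bars from the OLE early DBT discontinuers, subjects who fail the laboratory criteria at Week 12 (no repeats) and those already in follow-up when the OLE was added. Never-open-label placebo subjects are therefore few and partly selected on liver tests. Their timing also differs: a DBT completer is seen at about Weeks 12 + 2 = 14 and 12 + 8 = 20, an OLE completer at about Weeks 64 + 2 = 66 and 64 + 8 = 72.
- **Layouts may be settled elsewhere.** SAP 6.1.1 points to a separate mock TLF document and SAP 6.4.3 to the Core SAP. Neither is available here, so a footnote or subcolumn may already exist.

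**Conclusion.** The point holds as a presentation weakness in two descriptive tables. The follow-up rows of SAP 6.4.2.3 and 6.4.3.1 mix never-exposed and post-zavegepant subjects under PBO 100 mg and PBO 200 mg, although the SAP already has a layout that separates them. A permitted exception does not make the mixed column informative.

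On size, about 83% of placebo subjects would be post-OLE and about 17% of a contrast in mean change would remain. Both figures rest on planning counts, equal entry by arm and equal attendance; the 17% also needs the mixing model in step 6. With equal entry and attendance varied from 0.5 to 0.9, roughly 10% to 26% of the contrast remains. A reader might take 83% as the trial's actual share. The documents do not give that share: the OLE was added after some subjects had entered follow-up (Protocol 4.3.3), and the study was terminated early in December 2023 (SAP 1).

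A reader might also infer that post-treatment differences are hidden throughout the report. They are not: the contrast is diluted in these rows, while the follow-up AE, laboratory-abnormality, LFT-elevation and vital-sign abnormality tables are split by open-label status.

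**What to change.** In SAP 6.4.2.3 and 6.4.3.1, present the follow-up rows in Table 4's follow-up safety columns: placebo to open-label zavegepant by dose, placebo pooled with no open-label zavegepant, the zavegepant columns, and overall. Keep the double-blind columns for the baseline, on-DBT and on-OL rows. Give each follow-up column its own n and the baseline mean of the same subjects. If the present layout is kept, state it as an exception, give the reason, and footnote the number of open-label-exposed subjects in each placebo column.

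The cost is a wording change and a new column layout for the follow-up part of two tables. The grouping is already needed for the other follow-up tables, so no new derivation is required. The never-open-label placebo column will be small (about 80 on the planning figures with equal entry) and selected. A footnote should say that it is descriptive and not a randomized comparison. Table 4 does not split the zavegepant columns by OLE entry, so the change separates placebo subjects only.
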